5.2. Handling of missing data and drop-outs

This is a pilot study looking at physiological outcomes, thus it will be analyzed on a perprotocol basis. In the case of drop-outs, we will simply replace the participants.

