4.4 Withdrawal and discontinuation

We foresee the following reason for participants not to complete the study:

- Technical failure of the SESI-MS Ionization analytical platform
- Withdrawal of informed consent

In the case of withdrawal, the mass spectra and any material of the participant will be destroyed or deleted. In the case of drop-outs, we will replace the participants.

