4 STATISTICS AND METHODOLOGY

5.1. Statistical analysis plan and sample size calculation

This is a pilot study and no literature has been found on the topic of placebo and metabolomics that may allow for a reasonable sample size estimation. Thus, we employ a rule of thumb approach based on our experiences in previous metabolomics studies (Pablo Sinues, 2013). (Pablo Sinues Tarokh L, 2014)

All 20 participants will undergo two study visits. The order in which they will receive differs, with participants being randomly split into two groups via matlab randi function: 10 participants first CPT + placebo and then CPT, and 10 participants vice versa. Null and alternative hypotheses are formulated as follows:

- Null hypothesis: the mean difference concentration (i.e. signal intensity as proxy) of exhaled metabolites is equal in CPT and in CPT+placebo ($\mu_{CPT} = \mu_{CPT+Placebo}$)
- Alternative hypothesis: the mean difference concentration (i.e. signal intensity as proxy) of exhaled metabolites is significantly different in CPT and in CPT+ placebo ($\mu_{CPT} \neq \mu_{CPT+Placebo}$)

A two-way repeated measures ANOVA will be performed to evaluate the effect of different treatments (CPT and CPT + placebo) over time on exhaled metabolite abundance. False discovery rate for multiple testing will be taken care using established procedures (Storey, 2002). The preprocessing of the raw mass spectra and the statistical analysis will be implemented using MATLAB (MathWorks, Massachusetts, US).

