7.2 Risk-benefit assessment

The risks in taking part in this trial are minimal. The breath analysis is non-invasive as the participants simply exhale into a disposable mouthpiece. The CPT can be stopped by the probands as soon as they feel discomfort. Potential light-headedness by probands is under control by a medical doctor on site and a chair is provided if the probands need to rest.

There is no direct benefit to the project participants, however, studying the biological mechanisms of the placebo effects have a great and overarching impact into the broad field of clinical interventions. Amongst others, placebo effects tend to obscure efficacy of drugs. Any new tool to reduce this unwanted data variability, would benefit clinical trials as well as clinical practice and patient care. Furthermore, it may also reduce patient's exposure to drugs they might not need, henceforward reducing drug side-effects in overall population.

Defining who might respond to placebo and how this happens biologically is of great importance as those who are very likely to respond to placebo could be excluded from clinical trials to increase the chances for seeing a drug-specific effect.

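### Per-protocol analysis with simple replacement does not tie a replacement to the vacated sequence, so the 10/10 balance is unprotected, usable data are lost and drop-out is concealed

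*Protocol*

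**What the plan says.** Section 5.1 of the protocol plans a two-period crossover: "All 20 participants will undergo two study visits", with participants "randomly split into two groups via matlab randi function", giving "10 participants first CPT + placebo and then CPT, and 10 participants vice versa". The analysis named there is a two-way repeated measures ANOVA of treatment over time. It mentions neither period nor sequence.

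Section 5.2 fixes the analysis set and the handling of losses: "it will be analyzed on a perprotocol basis. In the case of drop-outs, we will simply replace the participants". The reason offered is that this is a pilot study of physiological outcomes. The per-protocol set is not defined further.

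Section 4.4 repeats the replacement rule and foresees two reasons for not completing: failure of the analytical platform and withdrawal of consent. It adds that "In the case of withdrawal, the mass spectra and any material of the participant will be destroyed or deleted". Neither section links a replacement to the sequence of the person replaced.

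**The concern.** Three consequences follow from these rules.

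- **Balance.** In a crossover analysed without a period term, equal sequence sizes are what cancel a period effect such as familiarity with the cold water at the second visit. Replacement with no link to the vacated slot leaves that balance to chance.
- **Lost data.** A participant with a sound first visit and a platform failure at the second has not withdrawn consent, yet is replaced and left out. The first-visit data would still inform the comparison of pain with no-pain measurements, a secondary endpoint in section 3.2.
- **Concealment.** Refilling to 20 completers, with deletion of data after withdrawal, means that completers and withdrawals cannot be compared. The sections do not ask for drop-outs to be counted by sequence, visit or reason. If people leave because of pain or because the spray did nothing for them, the final group is selected and the results would not show it. Section 3.2 also plans to compare placebo responders with non-responders, so the make-up of the final group matters.

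**Working it through.** **The plan's own figure.** The 20 participants cannot be reproduced by a formula. Section 5.1 says "we employ a rule of thumb approach based on our experiences in previous metabolomics studies" and gives no effect size, SD, power or drop-out rate. The 10/10 split is taken as stated.

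**Step 1: balance after replacement.** Assume a start at 10/10, d drop-outs falling at random across sequences, and a fresh 1:1 draw for each replacement. If k of the d losses come from the first sequence, balance is kept only when exactly k replacements enter it:

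P(10/10) = Σₖ [C(10,k)·C(10,d−k)/C(20,d)] × [C(d,k)/2^d]

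For d = 1 this is 1/2. For d = 4 it is (210·1 + 1200·4 + 2025·6 + 1200·4 + 210·1)/(4845·16) = 22170/77520 = 0.286. A simulation of 200,000 runs agrees to within rounding:

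| Drop-outs | Still 10/10 | 12/8 or worse |
|---|---|---|
| 1 | 50% | 0% |
| 2 | 38% | 12% |
| 4 | 29% | 27% |
| 6 | 24% | 35% |

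If each replacement takes the vacated sequence, the split is 10/10 for any number of drop-outs.

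**Step 2: what an unequal split does.** Let τ be the treatment effect and π the first-period minus second-period difference. The within-person contrast (placebo minus no placebo) has expectation τ + π in the placebo-first sequence and τ − π in the other. Its plain mean over 20 people is τ + π(n₁ − n₂)/20. The share of π left in the contrast is 2/20 = 10% at 11/9, 4/20 = 20% at 12/8 and 6/20 = 30% at 13/7.

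A period term removes this. Averaging the two sequence means gives (τ + π + τ − π)/2 = τ at any split. The variance is proportional to (1/n₁ + 1/n₂)/4, which is 0.0500 at 10/10 and 0.0521 at 12/8, so adjustment at 12/8 costs about 4% in variance.

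**Step 3: possible selection of completers.** The documents give no drop-out rate and no link between drop-out and pain, so both are assumed. Take cold tolerance as standard normal and let the log-odds of drop-out change by 1 to 2 per SD of tolerance. In a simulation of 1,000,000 draws, mean tolerance among completers shifts by 0.05 to 0.08 SD at 5% drop-out, 0.09 to 0.15 SD at 10% and 0.18 to 0.26 SD at 20%. This reaches the treatment contrast only through a correlation between tolerance and the individual effect. With an assumed correlation of 0.3 to 0.5:

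- 10% drop-out: 0.3 × 0.093 = 0.03 to 0.5 × 0.145 = 0.07 SD
- 20% drop-out: 0.3 × 0.176 = 0.05 to 0.5 × 0.264 = 0.13 SD
- drop-out unrelated to tolerance, as with platform failure: 0

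**The case against.** The strongest defence is that this is a small mechanistic pilot with no efficacy claim, and a completer analysis is a defensible choice there. A participant with one visit gives no within-person contrast, so including such people adds little to the primary comparison. Deletion is already tied to withdrawal in section 4.4 and is not ordered after technical failure. The slot given to a replacement could be settled in a randomisation list or analysis plan that is not shown. Silence does not mean that replacements will be drawn afresh. All of this stands and limits the size of the point. It does not remove it, because the completer rule and the replacement rule are stated, and first-visit data remain useful for the pain versus no-pain endpoint.

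A reader might go further and infer that the rule selects participants by cold tolerance. The protocol does not support that. Section 7.2 says "The CPT can be stopped by the probands as soon as they feel discomfort", and the test description in section 3.4 sets only a maximum immersion time. Early hand removal is therefore a valid test and not a drop-out, and platform failure has no evident link to tolerance.

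A reader might also infer that the randomised sequences are broken. They may become unequal, but the protocol does not say that they will.

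Nor is an upward bias established. The primary test is two-sided over many mass-to-charge features, with no predicted direction for any of them. Calculations in which drop-outs are exactly the worst responders give shifts of 0.109, 0.195 and 0.350 SD at 5%, 10% and 20% loss. The arithmetic is correct, but these are ceilings that rest on rates the documents do not give.

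**Conclusion.** The point holds as a gap in a stated rule. It does not show that the results will be biased. Sequence balance is unprotected: under a fresh 1:1 draw for replacements, 10/10 survives one drop-out with probability 50% and four with 29%. At 12/8, one fifth of any period difference would stay in a contrast with no period term. The size of such a difference is unknown, so the bias itself cannot be stated.

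Evaluable data from technical failures are discarded without need. The conclusion is confined to completers, whose possible selection cannot be examined afterwards. That selection has no known direction and is probably small (step 3), and it vanishes if losses are technical.

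**What to change.** In sections 4.4, 5.1 and 5.2:

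1. Give each replacement the sequence of the participant replaced.
2. Analyse all randomised participants with evaluable data who have not withdrawn consent, as randomised, in a mixed model with treatment, time, period and sequence as fixed effects and participant as a random effect. Define the per-protocol set and show the completer analysis as a sensitivity analysis.
3. Report the numbers of drop-outs and replacements by sequence, visit and reason. Counts can be kept even where the measurements are deleted.

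The cost is a few sentences and slightly more analysis work, with no participants beyond the replacements already planned. The gain has limits. One-visit participants add little to the within-person contrast. The model cannot recover information deleted after withdrawal of consent, so any selection by that route is made visible through the counts but not corrected.

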5 REGULATORY ASPECTS AND SAFETY

6.1 Local regulations / Declaration of Helsinki

This study is conducted in compliance with the protocol, the current version of the Declaration of Helsinki, the ICH-GCP the HRA as well as other locally relevant legal and regulatory requirements.

6.2 (Serious) Adverse Events and notification of safety and protective measures

An Adverse Event (AE) is any untoward medical occurrence in a patient or a clinical investigation subject which does not necessarily have a causal relationship with the trial procedure. An AE can therefore be any unfavourable or unintended finding, symptom, or disease temporally associated with a trial procedure, whether or not related to it.

A Serious Adverse Event (SAE) (ClinO, Art. 63) is any untoward medical occurrence that

- Results in death or is life-threatening,
- Requires in-patient hospitalisation or prolongation of existing hospitalisation,
- Results in persistent or significant disability or incapacity, or
- Causes a congenital anomaly or birth defect

Both Investigator and Sponsor-Investigator make a causality assessment of the event to the trial intervention, (see table below based on the terms given in ICH E2A guidelines). Any event assessed as possibly, probably or definitely related is classified as related to the trial intervention.

| Relationship | Description | |
|-------------------------------------|---|--|
| Definitely | Temporal relationship | |
| | mprovement after dechallenge* | |
| | Recurrence after rechallenge | |
| | (or other proof of drug cause) | |
| Probably | Temporal relationship | |
| | Improvement after dechallenge | |
| | No other cause evident | |
| Possibly | Temporal relationship | |
| | Other cause possible | |
| Unlikely | Any assessable reaction that does not fulfil the above conditions | |
| Not related | Causal relationship can be ruled out | |
| *Improvement after dechallenge only | taken into consideration, if applicable to reaction | |

Both Investigator and Sponsor-Investigator make a severity assessment of the event as mild, moderate or severe. Mild means the complication is tolerable, moderate means it interferes with daily activities and severe means it renders daily activities impossible.

Reporting of SAEs (see ClinO, Art. 63)

All SAEs are documented and reported immediately (within a maximum of 24 hours) to the Sponsor-Investigator of the study.

If it cannot be excluded that the SAE occurring in Switzerland is attributable to the intervention under investigation, the Investigator reports it to the Ethics Committee via BASEC within 15 days.

Follow up of (Serious) Adverse Events

Notification of safety and protective measures (see ClinO, Art 62, b)

If immediate safety and protective measures have to be taken during the conduct of the study, the investigator notifies the Ethics committee of these measures, and of the circumstances necessitating them, within 7 days.

6.3 (Periodic) safety reporting

An annual safety report (ASR/DSUR) is submitted once a year to the local Ethics Committee by the Investigator (ClinO, Art. 43 Abs).

6.4 Radiation

NA

6.5 Pregnancy

NA

6.6 Amendments

Substantial changes to the study setup and study organization, the protocol and relevant study documents are submitted to the Ethics Committee for approval before implementation. Under emergency circumstances, deviations from the protocol to protect the rights, safety and well-being of human subjects may proceed without prior approval of the Ethics Committee. Such deviations shall be documented and reported to the Ethics Committee as soon as possible.

A list of all non-substantial amendments will be submitted once a year to the competent EC together with the ASR.

6.7 (Premature) termination of study

The Sponsor-Investigator may terminate the study prematurely according to certain circumstances, e.g.

- Ethical concerns,
- Insufficient participant recruitment,
- When the safety of the participants is doubtful or at risk (e.g. when the benefit-risk assessment is no longer positive),
- Alterations in accepted clinical practice that make the continuation of the study unwise, or
- Early evidence of harm or benefit of the experimental intervention

Upon regular study termination, the Ethics Committee is notified via BASEC within 90 days (ClinO, Art. 38).

Upon premature study termination or study interruption, the Ethics Committee is notified via BASEC within 15 days (ClinO, Art. 38).

6.8 Insurance

In the event of study-related damage or injuries, the liability of the institution provides compensation, except for claims that arise from misconduct or gross negligence.

7 FURTHER ASPECTS

7.1 Overall ethical considerations

This project entails two main ethical considerations: The participants will be exposed to a hidden placebo and the discomfort the CPT will cause on the participants.

7.2 Risk-benefit assessment

The risks in taking part in this trial are minimal. The breath analysis is non-invasive as the participants simply exhale into a disposable mouthpiece. The CPT can be stopped by the probands as soon as they feel discomfort. Potential light-headedness by probands is under control by a medical doctor on site and a chair is provided if the probands need to rest.

There is no direct benefit to the project participants, however, studying the biological mechanisms of the placebo effects have a great and overarching impact into the broad field of clinical interventions. Amongst others, placebo effects tend to obscure efficacy of drugs. Any new tool to reduce this unwanted data variability, would benefit clinical trials as well as clinical practice and patient care. Furthermore, it may also reduce patient's exposure to drugs they might not need, henceforward reducing drug side-effects in overall population.

Defining who might respond to placebo and how this happens biologically is of great importance as those who are very likely to respond to placebo could be excluded from clinical trials to increase the chances for seeing a drug-specific effect.

8 QUALITY CONTROL AND DATA PROTECTION

8.1 Quality measures

For quality assurance the sponsor, the Ethics Committee or an independent trial monitor may visit the research sites. Direct access to the source data and all study related files is granted on such occasions. All involved parties keep the participant data strictly confidential.

8.2 Data recording and source data

A designated research fellow will be responsible for data collection and data management. Data are registered in a paper Case Report Form (CRF). Paper documents and informed consent forms will be stored in a lock-secured cupboard in a dedicated research office in the responsible laboratory (UKBB, Basel). Only study investigators have access to these documents. Authorized staff of the responsible ethics committee can request access to these data for monitoring and auditing purposes.

Scientific reports generated from the study will not contain information that would identify the participating persons. After termination of the study records and documents pertaining to the conduct of this study, including CRFs, consent forms, laboratory test results and clinical notes will be archived for ten years and then destroyed. The UKBB Division of Pediatric Pulmonology will handle administration of the study database. The data entry will be performed by the study team. Authorized staff of the responsible ethics committee can request access to these data for monitoring and auditing purposes. Electronic data will be stored on password-secured computers. Files will be stored within the UKBB intranet server. The data is securely stored on the hospital server in form of mass spectra, exhalion data, heartrate monitor data and logfile excel lists

(Appendix 8). Data can only be accessed by authorized users from registered computers at the UKBB. Source data will consist of coded mass spectra.

8.3 Confidentiality and coding

Trial and participant data will be handled with uttermost discretion and is only accessible to authorised personnel who require the data to fulfil their duties within the scope of the study. On the CRFs and other study specific documents, participants are only identified by a unique participant number.

All personal information obtained for this study is confidential and disclosure to third parties other than those noted below is prohibited. Confidentiality of the subjects will be maintained by assigning subjects a study number (ID), keeping identifiers separate from the data and storing data in a locked file and secure computer database in line with Swiss legal requirements. Patient identifier will be assigned with a consecutive number after the project acronym (e.g. CPT_001). All recorded electronic data (i.e. mass spectra, blood pressure, heartrate) will be coded with the patient identifier. These source data will be recorded in password-protected local computers and back-up in an external hard drive.

8.4 Retention and destruction of study data and biological material

No storage of biological material is foreseen. Records and documents pertaining the conduct of this study, including CRFs, consent forms, participant diaries and clinical notes will be retained for 10 years.

9 MONITORING AND REGISTRATION

The aim of monitoring is to evaluate the progress of the study, to verify the accuracy and completeness of CRFs, to ensure that all protocol requirements, applicable local authority regulations and investigator's obligations are being fulfilled, and to resolve any inconsistencies in the study records. Regular monitoring visits at the investigator's site prior to the start and during the course of the study will be performed by independent monitors not included in the research group. The monitoring is performed by [name] (experienced and GCP certified lead study nurse UKBB, USB). The source data/documents are accessible to monitors and questions are answered during monitoring

The study is registered with BASEC, the FOPH portal SNCTP (Swiss National Clinical Trial Portal) and clinicaltrials.gov.

10. FUNDING / PUBLICATION / DECLARATION OF INTEREST

This project will be supported by the Fondation Botnar via the Professorship of the principal investigator and the Swiss National Science Foundation (173168). The compensation of participants will be covered by the Division of Clinical Psychology and Psychotherapy, Faculty of Psychology, University of Basel, which also supports the study with PhD candidates and master students.

We plan to publish the results of this study in a peer reviewed journal. We also plan to present the results of this study at clinical conferences.

Authorship credit is based on 1) substantial contributions to conception and design, acquisition of data, or analysis and interpretation of data; 2) drafting the article or revising it critically for important intellectual content; and 3) final approval of the version to be published.

Each author should have participated sufficiently in the work to take public responsibility for appropriate portions of the content.

We declare no conflict of interest (independence, intellectual, financial, proprietary).

Appendix 1: Schedule of assessments

| Visit | 1 | 2 |
|---------------------------|--------|--------|
| Time | 60 min | 60 min |
| Oral information | + | + |
| IC 1 | + | |
| IC 2 | | + |
| Check inclusion-/ | + | |
| exclusion criteria | | |
| CPT | + | + |
| Self-Report Pain | + | + |
| Heart rate Monitoring | + | + |
| Blood Pressure Monitoring | + | + |
| Breath analysis | + | + |
| Placebo | | + |

(uploaded to BASEC system):

Appendix 2: IC 1&2

Appendix 3: Information zur Prüfsubstanz Appendix 4: Participant recruitment Flyer

Appendix 5: CRF Appendix 6: GC

Appendix 7: script 'medication'

Appendix 8: logfile data

Appendix 9: inclusion/exclusion checklist
